9.2.2 Secondary Endpoints

The secondary endpoints are defined in section 3.3.2. These will be analyzed using the ITT and PP samples.

- Proportion endpoints will be descriptively summarized using frequency tables with frequencies, percentages, and 95% confidence intervals. Chi-squared tests will be used for comparisons between operationally tolerant and non-tolerant participants.
- Time-to-event endpoints will be assessed using Kaplan-Meier survival estimates and associated two-sided 95% confidence intervals. Subjects lost to competing risks or lost to follow-up will be censored at the time of occurrence of these events.
- Continuous endpoints will be summarized using descriptive statistics (n, mean, standard deviation, median, minimum, maximum). T-tests will be used for comparisons between operationally tolerant and non-tolerant participants.
- Categorical endpoints will be summarized using counts (n) and percentages (%). Chi-squared tests will be used for comparisons between operationally tolerant and non-tolerant participants.

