3. GENERAL ANALYSIS AND REPORTING CONVENTIONS

The following analyses and reporting conventions will be used:

- Categorical variables will be summarized using counts (n) and percentages (%) and will be presented in the form “n (%).” Percentages will be rounded to one decimal place.
- Numeric variables will be summarized using n, mean, standard deviation (SD), median, minimum (min), maximum (max). The min/max will be reported at the same level of significance as original data. The mean and median will be reported at one more significant digit than the precision of the data, and SD will be reported at two more significant digits than the precision of the data.
- The median will be reported as the average of the two middle numbers if the dataset contains an even number of observations.
- Test statistics including t and z test statistics will be reported to two decimal places.
- P -values will be reported to three decimal places if greater than or equal to 0.001. If less than 0.001, the value will be reported as “<0.001.” A p -value can be reported as “1.000” only if it is exactly 1.000 without rounding. A p -value can be reported as “0.000” only if it is exactly 0.000 without rounding.
- Proportions will be expressed as percentages.
- Missing data will not be imputed unless explicitly stated.

If departures from these general conventions are present in the specific evaluations section of this SAP, then those conventions will take precedence over these general conventions.

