7.3. Secondary Endpoints

All secondary endpoints will be analyzed as described in Table 7-2. Mock displays for these results are outlined in the Appendix.

Table 7-2 Table of Endpoints and Analysis Methods

Endpoint	Method	Population
Primary		
The proportion of participants who achieve operational tolerance 52 weeks after completion of immunosuppression withdrawal.	Proportion of participants who achieve operational tolerance 52 weeks after completion of immunosuppression withdrawal with a corresponding two-sided 95% exact binomial confidence interval.	ITT, PP
Secondary		
Safety		
The proportion of participants who develop DSA or de novo anti-HLA antibodies after initiation of immunosuppression withdrawal.	Proportion of participants who develop DSA or de novo anti-HLA antibodies after initiation of immunosuppression withdrawal with a corresponding two-sided 95% exact binomial confidence interval.	ITT, PP
The incidence, severity, and timing of acute rejection, steroid resistant rejection, and chronic rejection.	
Acute Rejection: Incidence will be measured as the proportion of participants who have acute rejection (per Banff criteria) with a corresponding two-sided 95% exact binomial confidence interval.
 
Severity will be measured according to the Banff grade. Acute rejection can be expressed as mild, moderate or severe. This will be summarized descriptively with counts and percentages.
	ITT, PP
	
Steroid Resistant Rejection: Incidence will be measured as the proportion of participants who have steroid resistant rejection (rejection requiring antibody treatment) with a corresponding two-sided 95% exact binomial confidence interval.
 
All steroid resistant rejections are considered severe in nature and nothing further will be summarized.
	
	
Chronic Rejection: Incidence will be measured as the proportion of participants who have chronic rejection (per Banff criteria) with a corresponding two-sided 95% exact binomial confidence interval.
	

	
Severity will be measured according to the Banff grade. Chronic rejection can be expressed as early or late. This will be summarized descriptively with counts and percentages.
 
For all rejection types, timing will be expressed as the time from the initiation of immunosuppression withdrawal to the time of the first biopsy showing acute rejection and will be summarized descriptively.
 
All data presented will use the central read.

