13. APPENDIX

Table X. Safety Endpoints

	Total (N = XX)
Development of DSA or de novo anti-HLA antibodies, n (%)	X (X.X%)
95% Exact Binomial Confidence Interval	(X.X, X.X)
Incidence of acute rejection, n (%)	X (X.X%)
95% Exact Binomial Confidence Interval	(X.X, X.X)
Severity of acute rejection per Banff criteria, n (%)	
Mild	X (X.X%)
Moderate	X (X.X%)
Severe	X (X.X%)
Time to first acute rejection, median (IQR)	X.X (X-X)
Incidence of steroid resistant rejection, n (%)	X (X.X%)
95% Exact Binomial Confidence Interval	(X.X, X.X)
Time to first steroid resistant rejection, median (IQR)	X.X (X-X)
Incidence of chronic rejection, n (%)	X (X.X%)
95% Exact Binomial Confidence Interval	(X.X, X.X)
Severity of acute rejection per Banff criteria, n (%)	
Early	X (X.X%)
Late	X (X.X%)
Time to first chronic rejection, median (IQR)	X.X (X-X)
Graft Loss, n (%)	X (X.X%)
95% Exact Binomial Confidence Interval	(X.X, X.X)
All-cause Mortality, n (%)	X (X.X%)
95% Exact Binomial Confidence Interval	(X.X, X.X)
Study-related Serious Adverse Events, n (%)	X (X.X%)
95% Exact Binomial Confidence Interval	(X.X, X.X)

Table X. Long-term Tolerance

	Total (N = XX)
Tolerant Subjects Free of Rejection 3 years after Completing Immunosuppression Withdrawal, n (%)	X (X.X%)
95% Exact Binomial Confidence Interval	(X.X, X.X)

Table X. Graft Fibrosis in Tolerant vs. Non-tolerant Subjects

	Tolerant (N = XX)	Non-tolerant (N = XX)	Total (N = XX)
Graft Fibrosis, n (%)			
ISHAK	X (X.X%)	X (X.X%)	X (X.X%)
LAFsc	X (X.X%)	X (X.X%)	X (X.X%)
95% Exact Binomial Confidence Interval			
ISHAK	(X.X, X.X)	(X.X, X.X)	(X.X, X.X)
LAFsc	(X.X, X.X)	(X.X, X.X)	(X.X, X.X)
Change from Eligibility Biopsy to End of Study Biopsy, median (IQR)			
ISHAK	X.X (X-X)	X.X (X-X)	X.X (X-X)
LAFsc	X.X (X-X)	X.X (X-X)	X.X (X-X)

Table X. GFR in Tolerant vs. Non-tolerant Subjects

	Tolerant (N = XX)	Non-tolerant (N = XX)	Total (N = XX)
Change in eGFR ^[1] , median (IQR)			
Year 1	X.X (X-X)	X.X (X-X)	X.X (X-X)
Year 2	X.X (X-X)	X.X (X-X)	X.X (X-X)
Year 3	X.X (X-X)	X.X (X-X)	X.X (X-X)

[1] Estimated GFR (eGFR) is calculated by the CKD-EPI method.

Table X. Quality of Life Measures in Tolerant vs. Non-tolerant Subjects

	Tolerant (N = XX)	Non-tolerant (N = XX)	Total (N = XX)
Change in SF-36 ^[1] , median (IQR)			
Physical Component Score (PCS)	X.X (X-X)	X.X (X-X)	X.X (X-X)
Mental Component Score (MCS)	X.X (X-X)	X.X (X-X)	X.X (X-X)
Change in NIDDK ^[1] , median (IQR)			
Measures of Disease	X.X (X-X)	X.X (X-X)	X.X (X-X)

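### SAP Table 7-2 dates every type of rejection by the first acute-rejection biopsy, and timing is an event-only median where Protocol 9.2.2 calls for Kaplan-Meier

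*SAP*

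**What the plan says.** Protocol 3.3.2 lists incidence, severity and timing of acute, steroid-resistant and chronic rejection as one secondary safety endpoint. SAP 7.3 states: "All secondary endpoints will be analyzed as described in Table 7-2". Within that table a single timing rule is set for every type of rejection: "timing will be expressed as the time from the initiation of immunosuppression withdrawal to the time of the first biopsy showing acute rejection". The result is to be summarised descriptively, using the central read.

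The mock safety table in the SAP appendix gives each type its own timing row. Besides the acute row there are "Time to first steroid resistant rejection, median (IQR" and "Time to first chronic rejection, median (IQR" (closing brackets cut). No confidence interval is attached to any of them. In the same table the Early and Late rows for chronic rejection sit under the heading "Severity of acute rejection per Banff criteria, n".

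Protocol 9.2.2 says of secondary endpoints: "Time-to-event endpoints will be assessed using Kaplan-Meier survival estimates and associated two-sided 95% confidence intervals". It adds: "Subjects lost to competing risks or lost to follow-up will be censored at the time of occurrence of these events". The SAP text available contains no Kaplan-Meier estimate and no censoring rule. Its section 11, meant for changes from the protocol's analyses, shows only a heading.

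**The concern.** There are two faults in one endpoint.

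**Dating.** A clock that stops at an acute-rejection biopsy cannot measure time to chronic rejection. One programmer working from Table 7-2 and another from the shell would produce different chronic-rejection times from the same data.

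**Summary.** A participant who never rejects has no stop date and so no time. A median of the recorded times therefore describes only those who rejected. Printed without a label, it can be read as the time by which half of all participants had rejected. That is a different quantity, and it may not exist in this trial.

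Protocol 1.4.1.1 calls graft rejection the main risk of withdrawal, so when it occurs is safety information that readers will use.

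**Working it through.** The plan states no figure for rejection timing, so there is none to reproduce. The check compares the texts and then sizes the consequences.

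**1. Table 7-2 against the shell**

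| Participant's history | Chronic-rejection time under Table 7-2 | Under the shell row |
|---|---|---|
| Acute, later chronic | Start of withdrawal to acute biopsy | Start of withdrawal to first chronic biopsy |
| Chronic only | No date | Start of withdrawal to first chronic biopsy |

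Steroid-resistant rejection is less clear-cut. Protocol 6.8 treats it as a form of acute rejection, so an acute biopsy is a defensible onset. The first acute biopsy may still belong to an earlier, separate episode.

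**2. Size of the dating error.** Under Protocol 6.8, a participant who rejects after completing withdrawal stays on Appendix 2, which has protocol biopsies at weeks 52 and 156. Both dates share the same start, so the error is the chronic date minus the acute date. At nominal times, ignoring visit windows, with acute rejection at weeks 0 to 52:
- Chronic first seen at week 156: 156 − 52 = 104 to 156 − 0 = 156 weeks too early.
- Chronic first seen at week 52: up to 52 − 0 = 52 weeks too early.

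Appendix 3 has no protocol biopsies, so no such range can be given for participants who fail during withdrawal.

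**3. Does Protocol 9.2.2 apply?** It names no endpoint. Rejection is the only secondary endpoint in Protocol 3.3.2 that lists timing, and Table 7-2 analyses graft loss and mortality as proportions. If the rule does not cover rejection timing, no endpoint in Table 7-2 receives it.

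**4. Event-only median against Kaplan-Meier.** Inputs: N = 60 (Protocol 9.3); 50% rejection (Protocol 1.4.1.1); 58%, from 57 of 98 (Protocol 1.3.1, a cohort that included HCV-positive recipients, who are excluded here). I add 40% as an assumption. It is the most that could have rejected by the primary endpoint if 60% prove tolerant, the second scenario in Protocol 9.3.

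Without censoring, a Kaplan-Meier median exists only if at least 30 of 60 reject:

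| Rejection probability | Expected rejectors | P(X ≥ 30), X ~ Bin(60, p) |
|---|---|---|
| 0.40 | 24 | 0.075 |
| 0.50 | 30 | 0.551 |
| 0.58 | 34.8 | 0.916 |

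The event-only median is printed in every case. Protocol 9.2.2 asks for survival estimates with intervals, not specifically a median. With 30 of 60 rejected by a fixed time and no censoring, the estimate would be 50%, exact 95% CI 36.8% to 63.2%.

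Where both medians exist, let c be the proportion rejecting by the horizon. The event-only median solves F(t) = c/2; the Kaplan-Meier median solves F(t) = 0.5. For a Weibull curve with shape k,

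ratio = [ln(1 − c/2) / ln(0.5)]^(1/k).

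| c | k = 0.5 | k = 1 (constant hazard) | k = 2 | k = 4 |
|---|---|---|---|---|
| 0.50 | 0.172 | 0.415 | 0.644 | 0.803 |
| 0.58 | 0.244 | 0.494 | 0.703 | 0.838 |

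As an illustration in weeks, take a horizon of 45 + 52 = 97 weeks and event times spread evenly over it. The event-only median is 48.5 weeks. The Kaplan-Meier median is 97.0 weeks with 30 of 60 rejecting and 83.1 weeks with 35 of 60.

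**The case against.** The strongest reply is that the dating fault is one wrong word. The shell shows what was meant, and nobody would knowingly fill a chronic-rejection row with an acute date. Few participants are likely to be affected: Protocol Table 2 suspends the study at 6 of 60 with severe acute, refractory or chronic rejection, and SAP 8.5.3.4 lists those events individually. All of this is fair, and the documents give no expected number of chronic events. The governing sentence is still wrong, and the shell has a slip of its own in the Early/Late heading, so neither text can simply be trusted over the other.

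On the summary, Protocol 9.2.2 may be generic wording, and it also has a bullet for continuous endpoints. Protocol 9.2 leaves detail to the SAP, and text under SAP section 11 may have been lost in extraction. The Kaplan-Meier conflict is therefore an inference, though the natural one. The SAP convention "Missing data will not be imputed unless explicitly stated" adds little, because never having rejected is not missing data. The median is event-only because the clock ends on a biopsy and there is no censoring rule. Incidence with an exact interval appears in each type's block above the timing row, which reduces the risk of misreading but does not remove it.

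The Weibull ratios are not bounds. A tolerant fraction that never rejects would change the curve's shape and hence the ratio. They show direction and rough scale only.

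**Conclusion.** The concern holds. As written, Table 7-2 misdates chronic rejection or leaves it undated, and it cannot produce the shell's chronic row. The error is 104 to 156 weeks per affected participant in the year-3 sequence above; how many would be affected is unknown.

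The timing summary rests on participants with the event, about 30 of 60 at 50% rejection, and omits the estimate over time, its interval and its censoring. That departs from Protocol 9.2.2 on its evident reading, and no declared change is visible. Where a Kaplan-Meier median exists, the event-only median comes earlier, by an amount the documents cannot fix.

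This should be corrected before analysis. It concerns a named secondary safety endpoint only; the primary endpoint and sample size stand.

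**What to change.** - Define the stop date by type in Table 7-2: for acute and chronic rejection, the first centrally read biopsy showing that type; for steroid-resistant rejection, one stated date, either the onset of that episode or the date resistance is established.
- Report Kaplan-Meier estimates from the start of withdrawal over the ITT sample, with 95% confidence intervals and the censoring in Protocol 9.2.2. Give estimates at fixed times where the median is not reached. If cumulative incidence is used instead, treat competing events as competing, not censored.
- Say how participants who stop withdrawal or restart immunosuppression without rejection are handled; they can stay at risk. Note beside the display that Appendix 3 has no protocol biopsies, so subclinical rejection is less likely to be detected there.
- Label any event-only median as applying to participants with the event.
- Correct the heading over the Early/Late rows to chronic rejection.
- Record any departure from Protocol 9.2.2 in SAP section 11; Protocol 9.5 requires an amendment for changes to principal features of the analysis.

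The cost is SAP wording, one heading and one display from data already collected.

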Portal inflammation and interface activity	This is preferably absent, but minimal to focal mild portal mononuclear inflammation may be present. Interface necro-inflammatory activity is absent or equivocal/minimal and, if present, involves a minority of portal tracts and not generally associated with fibrosis.
Centrilobular/perivenular inflammation	Negative for perivenular inflammation.
Bile duct changes	Lymphocytic bile duct damage, ductopenia, and biliary epithelial senescence changes are absent unless there is an alternative, non-immunological explanation (e.g. biliary strictures).
Fibrosis**	Fibrosis (if present) should be mild overall, and portal-to-portal bridging should not be more than rare. Perivenular and peri-sinusoidal fibrosis should not be more than mild according to the Banff criteria.
Arteries	Findings for obliterative or foam cell arteriopathy are negative.

*Patients with underlying AIH, HCV, PBC, or PSC are excluded⁴.

**Fibrosis should be graded as follows⁶⁷:

- **Portal/periportal:** 0 – 3
- **Peri-sinusoidal:** 0 – 3
- **Perivenular:** 0 – 3

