6.10 LIVER BIOPSY

6.10.1 Types of Biopsies

- Protocol Biopsies

- Participants will undergo liver biopsies at times specified in the schedule of events (see Appendices 1 and 2). These biopsies will be used to monitor liver function, to screen for subclinical rejection, and for mechanistic analyses.
- For-cause Biopsies
 - For-cause biopsies (FCB) will be obtained to confirm suspected rejection following unexplained allograft dysfunction (see Section 6.6 for definition) and all mechanistic assessments listed in Appendix 5 should be performed.

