APPENDIX 2. SCHEDULE OF EVENTS – POST WITHDRAWAL FOLLOW-UP

IMPORTANT NOTE: For the duration of the COVID-19 pandemic, follow the COVID-19 Modified Appendix 2-C instead (per Section 6.2).

IS Withdrawal Follow-up Weeks ¹	0	13	26	52	78	104	130	156
Visit Number ^{2,3}	201 ⁴	202	203	204	205	206	207	208
General Assessments								
Limited physical exam	X	X	X	X	X	X	X	X
Vital signs including weight	X	X	X	X	X	X	X	X
Quality of Life Questionnaires	X		X	X	X	X	X	X
Status Change since prior visit ⁵	X	X	X	X	X	X	X	X
Telephone consultation ⁶	X							X
ECG					Prior to restarting tacrolimus ⁷			
Local Clinical Laboratory Assessments								
LFTs ⁸		Every 4 weeks		Every 8 weeks			Every 12 weeks	
CBC w/differential	X	X	X	X	X	X	X	X
Comprehensive metabolic panel, includes LFTs	X	X	X	X	X	X	X	X
Liver biopsy				X				X
Mechanistic Laboratory Assessments								
Frozen PBMC collection	X		X	X		X		X
Serum collection	X		X	X		X		X
Whole blood collection	X		X	X		X		X
Urine pellet collection	X		X	X		X		X
Fecal collection ⁹	X		X	X		X		X
Liver biopsy collection				X				X

¹ The assessments outlined in Appendix 2 should be completed for all participants who initiated and successfully completed immunosuppression withdrawal. Follow-up should begin within 2 weeks of the date of completion of the participant's last taper level (see section 3.1.3).

² If a for-cause liver biopsy is needed, follow all assessments specified in Appendix 5. If the for-cause biopsy occurs within 8 weeks prior to a scheduled protocol visit, complete all clinical and mechanistic assessments listed in Appendix 5 at the time of the for-cause biopsy. The for-cause biopsy visit will take the place of the scheduled protocol visit.

³ If a participant restarts immunosuppression after successfully completing immunosuppression withdrawal, follow the assessments listed in Appendix 4. **Appendix 2 visits to be completed in addition and concurrently with Appendix 4.**

⁴ For any participant requesting early termination from the study, follow all assessments specified here, Visit 201.

⁵ Includes assessment of change in adverse events and concomitant medications. Changes should be recorded in eCRFs as appropriate.

⁶ Complete following the performance of each liver function test assessment done outside of a transplant center clinical visit; AEs and concomitant medications to be reviewed.

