APPENDIX 3. SCHEDULE OF EVENTS – SAFETY FOLLOW-UP

IMPORTANT NOTE: For the duration of the COVID-19 pandemic, follow the COVID-19 Modified Appendix 3-C instead.

Safety Follow-up Weeks ¹	0	13	26	52	104	156
Visit Number ²	301 ^{3,4}	302	303	304	305	306
General Assessments						
Limited Physical Exam	X	X	X	X	X	X
Vital signed including weight	X	X	X	X	X	X
Quality of Life Questionnaires	X		X	X	X	X
Status Change since prior visit ⁵	X	X	X	X	X	X
Telephone consultation ⁶	X					X
ECG			Prior to restarting tacrolimus if on MMF monotherapy ⁷			
Local Clinical Laboratory Assessments						
LFTs ⁸		Every 4 weeks		Every 8 weeks		Every 12 weeks
CBC w/differential	X	X	X	X	X	X
Comprehensive metabolic panel, includes LFTs	X	X	X	X	X	X
Mechanistic Laboratory Assessments						
Frozen PBMC collection	X		X	X	X	X
Serum collection	X		X	X	X	X
Whole blood collection	X		X	X	X	X
Urine pellet collection	X		X	X	X	X
Fecal collection	X		X	X	X	X

¹ The assessments outlined in Appendix 3 should be completed for all participants who initiated but did not complete immunosuppression withdrawal. Follow-up should begin within 2 weeks of the date of immunosuppression withdrawal failure (see section 3.1.3.5).

² If a for-cause liver biopsy is needed, follow all assessments specified in Appendix 5. If the for-cause biopsy occurs within 8 weeks prior to a scheduled protocol visit, complete all clinical and mechanistic assessments listed in Appendix 5 at the time of the for-cause biopsy. The for-cause biopsy visit will take the place of the scheduled protocol visit.

³ If a for-cause liver biopsy visit took place within 8 weeks of visit 301, all mechanistic assessments listed in Appendix 5 at the time of the for-cause biopsy visit should be completed in lieu of mechanistic assessments listed for visit 301.

⁴ For any participant requesting early termination from the study, follow all assessments specified here, Visit 301.

⁵ Includes assessment of change in adverse events and concomitant medications. Changes should be recorded in eCRFs as appropriate.

⁶ Complete following the performance of each liver function test assessment done outside of a transplant center clinical visit; AEs and concomitant medications to be reviewed.

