The incidence and progression of graft fibrosis in tolerant versus non-tolerant patients.	
Fibrosis will be looked at in two ways—by ISHAK ITT, PP and LAFSc.
 
ISHAK is a measure taken directly from the central pathology read.
 
LAFSc is calculated as the sum of three measures that summarize fibrosis in the portal tract (portal_fibrosis per central read), sinusoids (disse_fibrosis per central read), and centrilobular vein (central_fibrosis per central read).
 
For both ISHAK and LAFSc, a subject will be considered as having graft fibrosis if the score is greater than or equal to 2.
 
Incidence of graft fibrosis will be summarized descriptively with a proportion and corresponding two-side 95% exact binomial confidence interval using Ishak Score and LAFSc, separately, for tolerant and non-tolerant subjects.
 
Change in ISHAK score from baseline biopsy to the last available biopsy will be calculated. Descriptively statistics will be calculated separately for tolerant and non-tolerant subjects. This same process will be repeated for LAFSc.
 
All scores utilized will be from the central read.

The incidence of graft loss.	Proportion of participants who have lost their liver graft with a corresponding two-sided 95% exact binomial confidence interval. ITT, PP
The incidence of all-cause mortality.	Proportion of participants who have died with a corresponding two-sided 95% exact binomial confidence interval. ITT, PP

The incidence of study-related SAEs.	Proportion of study-related SAEs as assessed by the NIAID Medical Monitor with a corresponding two-sided 95% exact binomial confidence interval.	ITT, PP
Efficacy		
The proportion of operationally tolerant subjects who remain free of rejection at 3 years after completing immunosuppression withdrawal.	Proportion of tolerant participants who remain off all IS and free of rejection 3 years after completing immunosuppression withdrawal with a corresponding two-sided 95% exact binomial confidence interval.	Tolerant Subjects

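### Graft fibrosis incidence can include fibrosis present at entry, and the tolerant versus non-tolerant change score mixes biopsy times and reasons for participants who fail during withdrawal

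*SAP*

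**What the plan says.** **Incidence.** In SAP 7.3, Table 7-2, the case rule for both scores is that "a subject will be considered as having graft fibrosis if the score is greater than or equal to 2". The proportion is reported as incidence with an exact 95% interval, separately for tolerant and non-tolerant participants. On construction of the second score: "LAFSc is calculated as the sum of three measures that summarize fibrosis in the portal tract", the sinusoids and the centrilobular vein.

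**Fibrosis allowed at entry.** Protocol 4.2.1, Table 3 states: "Fibrosis (if present) should be mild overall, and portal-to-portal bridging should not be more than rare". It adds: "Perivenular and peri-sinusoidal fibrosis should not be more than mild according to the Banff criteria". Each of the three compartments is graded 0 to 3.

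**Progression.** Table 7-2 states: "Change in ISHAK score from baseline biopsy to the last available biopsy will be calculated", and repeats this for LAFSc, summarised by tolerance status. The shell in SAP section 13 instead labels the row as change from the eligibility biopsy to the end-of-study biopsy. SAP 7.1.2 uses all data whatever their timing unless a section says otherwise, and the fibrosis row does not.

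**Biopsy schedule.** Protocol 6.10.1 places protocol biopsies in Appendices 1 and 2.
- Appendix 2 has biopsies at weeks 52 and 156 and covers this group: "The assessments outlined in Appendix 2 should be completed for all participants who initiated and successfully completed immunosuppression withdrawal". The pandemic version, 2-C, lists week 156 only.
- Appendix 3 has no biopsy row, nor does 3-C. Its scope: "The assessments outlined in Appendix 3 should be completed for all participants who initiated but did not complete immunosuppression withdrawal".

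**The concern.** Two separate problems affect one safety endpoint.

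First, incidence should count new fibrosis. The rule as written counts any score at or above the threshold, so a participant who enters with such a score and never changes can be a case. The reader could not tell fibrosis that arose during or after withdrawal from fibrosis that was already there.

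Second, the change score compares groups whose last biopsies are obtained differently. Participants who complete withdrawal have scheduled biopsies up to three years later. Those who fail during the taper contribute a for-cause biopsy or nothing. A difference in progression, or the lack of one, could then reflect when and why the tissue was taken.

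This matters because fibrosis off immunosuppression is a safety question that the protocol itself raises. Protocol 3.4 advises caution about an earlier histology study because its groups differed in time since transplant. The Table 7-2 rule allows a comparable mismatch.

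**Working it through.** **1. The plan's own durations.** Protocol 3.2 gives 188 to 235 weeks per participant. These reproduce: 8 + 24 + 156 = 188 and 8 + 45 + 182 = 235. The 24 and 45 weeks for withdrawal are used below. No rate, power or sample size is stated for fibrosis.

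**2. Can an eligible participant score 2 or more at entry?**
- LAFSc = portal + sinusoidal + centrilobular grade.
- Assume mild = grade 1; the documents give no mapping. Table 3 lets the perivenular and peri-sinusoidal compartments both be mild, so 0 + 1 + 1 = 2, which meets the threshold.
- Of the 8 patterns with each compartment at 0 or 1, 4 have a sum of at least 2 (maximum 3). This counts patterns; it is not a probability.
- The mapping is not secure. Protocol 6.10.3 uses a scale with a minimal level below mild, rare bridging is also admitted, and the mild-overall wording might exclude some patterns. The count therefore shows that the overlap is possible and bounds nothing.
- For Ishak the documents do not define the stages. A score of 2 at entry is plausible but cannot be shown.

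Illustration only, with every input assumed: if a share p has a score of 2 or more at entry and keeps it, and a share i of the rest is new, the reported proportion is p + (1 − p) × i.

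| p | i | Reported | New onset among those at risk |
|---|---|---|---|
| 10% | 5% | 14.5% | 5% |
| 10% | 10% | 19.0% | 10% |
| 30% | 5% | 33.5% | 5% |
| 30% | 10% | 37.0% | 10% |

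**3. Who has which biopsies?**

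| Participant | Tolerance status | Scheduled biopsies after baseline |
|---|---|---|
| Completes, tolerant | Tolerant | Weeks 52 and 156 |
| Completes, later rejects (Protocol 6.8) or fails on week-52 histology (6.9) | Non-tolerant | Weeks 52 and 156 |
| Fails during withdrawal | Non-tolerant | None; for-cause (6.6.1) or none |

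The non-tolerant group is thus itself a mixture. A participant with presumed rejection who cannot have a biopsy counts as a failure (Protocol 3.1.3.5) and may have no post-baseline tissue.

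**4. How far apart are the last biopsies?** Weeks are counted from the start of withdrawal, with the ±4-week window of Protocol 6.1.1.
- Biopsy at taper failure: at most about 45.
- Earliest week-156 protocol biopsy: 24 + 156 − 4 = 176. Difference: 176 − 45 = 131 weeks, about 2.5 years.
- Earliest week-52 protocol biopsy: 24 + 52 − 4 = 72. Difference: 72 − 45 = 27 weeks.
- For-cause biopsies that replace a visit up to 8 weeks early lower these figures: 24 + 148 − 45 = 127 and 24 + 44 − 45 = 23.

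The screening biopsy precedes withdrawal by up to 9 weeks (56 + 7 = 63 days) in either group, or longer if an earlier biopsy is reused on rescreening (Protocol 6.4.1).

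**The case against.** **The shell may govern.** If the end-of-study label means the week-156 biopsy, most taper failures contribute no change score and the timing mismatch largely disappears. This is fair: the progression point holds under the Table 7-2 text. But the two SAP texts then disagree on what is calculated, and that needs settling in any case.

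**The summary is descriptive.** The SAP plans no p-values here, and Protocol 9.2 leaves the detail to the SAP. This stands, so the harm is a misleading contrast and not an inflated error rate. Yet the endpoint is worded as tolerant versus non-tolerant, the shell sets the groups side by side, and Protocol 9.2.2 names chi-squared and t-tests for such comparisons.

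**Missing biopsies are a design limit.** This is true, and SAP wording cannot create tissue. For eGFR the SAP aligns both groups at 1, 2 and 3 years after completion or failure, but blood tests are scheduled for both groups and biopsies are not. The SAP can still show timing and biopsy type.

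**Stronger readings that the documents do not support:**
- *That 131 weeks is a minimum gap between tolerant and non-tolerant participants.* It separates taper failures biopsied last at failure from completers with a week-156 protocol biopsy. It falls to about 27 weeks if the completer has only week 52, and a later for-cause biopsy in a taper failure shortens it.
- *That the planned contrast is circular because a fibrosis rise defines non-tolerance.* Table 7-2 plans no week-52 contrast. At present the overlap touches only participants whose last biopsy is the week-52 one. It becomes relevant to a week-52 row, if one is added.
- *That the illustration measures the inflation in this trial.* Its inputs are assumed.

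**Conclusion.** The concern holds in two parts.

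**Incidence.** As defined, the figure can include prevalent fibrosis. The missing baseline condition and unnamed biopsy apply to both scores. That an eligible participant can already meet the threshold is shown for LAFSc if mild is grade 1, and is only plausible for Ishak. The size is unknown because the documents give no entry distribution. The change score subtracts baseline, so it is not affected by this part.

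**Progression.** Under the Table 7-2 text, the contrast mixes observation times and biopsy reasons for participants who fail during withdrawal. The difference is at least about 131 weeks against a completer's week-156 protocol biopsy, or about 27 weeks against a week-52 biopsy only, if the taper failure's last biopsy is at failure. The share of non-tolerant participants in this position is unknown in advance.

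A reader might infer that the comparison is biased against tolerant participants because they are followed longer. The documents do not support a direction: biopsies taken because of suspected rejection could push the other way.

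**What to change.** Amend SAP text and table shells only.

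1. **Incidence.** Count a new score of 2 or more among participants with a baseline score below 2 and at least one post-baseline biopsy. Name the index biopsy. By group, report baseline prevalence, the at-risk denominator and the number without a follow-up biopsy. If the index is the last available biopsy, it carries the same unequal follow-up as the change score and should be read with the timing rows in item 2.
2. **Progression.** Reconcile the last-available wording in Table 7-2 with the end-of-study label in the shell. Keep the planned summary, and beside it show by group the time from baseline and the biopsy type (protocol or for-cause).
3. **Fixed times.** Add change at the week-52 and week-156 biopsies for Appendix 2 participants by tolerance status, with the numbers contributing. At week 52, use the same biopsy that determines the primary endpoint, and flag any that is out of window or for-cause. Show for-cause biopsies of taper failures separately.
4. **Footnote to the added week-52 row.** State that a rise of more than one grade in a compartment at that biopsy is itself a Table 1 failure criterion.

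The cost is an SAP amendment with the review named in Protocol 9.5. No biopsies are added. The drawback is that few non-tolerant participants may contribute at the fixed times, so those rows will be imprecise.
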